### **Power for Secondary Outcomes:**

For Aim 3, under the assumptions that our SDC group would have a proportion of 0.79 of people going to more than 75% of their scheduled visits, we calculated the size of change in the proportion of people receiving 75%+ visits in the OTC group that we would be able to detect with a significance level of 0.05 (two-tailed proportion test), power of 0.80, and varying the sample size from 100 to 900.

With 80% power, we would be able to statistically detect a proportion in the OTC group of 0.91 with a sample of 300 individuals, 0.88 with a sample size of 500, and of 0.86 with 900 (see graph below).

[figure not shown]
[figure not shown]
We will also test differences in number of hospitalizations, number of emergency department visits, and number of unplanned outpatient visits per year. These outcomes will be compared using a Poisson model. For the power analysis, we adjusted the significance level to 0.017 after using Bonferroni adjustment (0.05/3), and we considered sample sizes of 300, 500, 700, and 900. We considered the base rates of 1-4 events per year for the SDC group and calculated the power of detecting a decrease in that rate from 10% to 50% in the OTC group. Using G\*Power and the specifications above, the summary of the findings are as follows:

- The higher the base rate for the SDC group, the higher the power to find a difference;
- Power is at least 80% to find a decrease of 20% in the number of events, except when the base rate is 1, in which case the decrease would need to be 22-25% to be detected;
- Attrition or low enrollment (represented by sample sizes of 300, 500 and 700) have an effect but might be important only for a small base rate (such as 1 visit/year) and sample size 300 (unlikely to happen);
- Power for secondary analysis will be high to find a decrease of 20% in mean number of events (equivalent to odds ratio of .8 when comparing the OTC to the SDC group), except for sample lower than 500 (which is unlikely to happen).

The graphs below show the power for each base rate (odds ratio in x-axis and power in the y-axis).

[figure not shown]
[figure not shown]
Base rate = 1

Base rate = 2

[figure not shown]
Base rate = 3

Base Rate = 4

For Aim 4, for caregiver outcome, we assumed the following parameters:

- Sample sizes from 250 to 600 (by 50);
- Significance level of 0.05,
- SD=13 for both groups (based on the higher SD in Powell et al.),
- T-test (two-tailed)
- Change in Bakas Caregiving Outcome Scale (BCOS) from 56 in SDC group to at least 59 in the OTC group, corresponding to at least 5% increase in the BCOS (effect sizes of 0.25 or more).

At the moment we have 142 caregivers and if we continue to enroll in the same rate, we will have about 471 caregivers by the end of the study. For that sample size, except when the effect size is smaller than 0.3, we will be able to detect a change in BCOS. If the effect size is larger, we will be able to detect it with 80% power even for smaller sample sizes (350 for an effect of at least 0.3, 275 for an effect of at least 0.35, and 250 for an effect of at least 0.4). For the smallest effect size of 0.25, we would need to have about 500 caregivers for a power of 80% to find that small difference. Given our current estimates of the total sample size for the caregivers, we are likely to have power to find a difference, if the difference exists.

---

### **Data Analysis Plan Specific to Each Aim (IR-3, IR-5)**

**General approach:** The expected sample size is very large and we anticipate 100% power to find a difference in PART-O-17, if a difference exists. In addition, the sample size will allow us adequate power to examine our other aims and heterogeneity of treatment effects. We will use a significance level of 0.05 for all the analyses we will perform. Given the large sample size and the extremely high power for the primary outcome, we will not adjust the significance level for multiple comparisons for all the other tests, since it is highly likely that the p-values for those tests will be small. As it is well known and now stated in a publication by the American Statistical Association, the p-value should not be the single deciding measure of the significance of a result. Therefore, we will interpret the results of all non-primary outcomes with caution and will examine effect sizes as well as explicitly report the secondary outcomes status when presenting the results. We will obtain input from our stakeholders regarding the meaningfulness and importance of the effects.

The analysis plan will conform to the intent-to-treat principle: all randomized cases will be included based on their assigned treatment group regardless of actual intervention received. Missing values will be prevented and minimized by implementing the following steps in the manual of operations: 1) Prompt data entry to allow timely detection of any missing data, 2) Procedures for monitoring and tracking data completeness will be in the manual of operations, 3) When missing data are identified, research staff will contact the participant to collect them (if not time-contingent or outside the specified time range for collection). At the end of the study, participants not assessed at the end of intervention will be considered as having missing outcome values.

When missing values are present we will check the missing mechanism, and if it allows for imputation, we will do so according to the appropriate methods for a continuous variable, using multiple imputation strategies (most likely using maximum likelihood methods). We will perform sensitivity analysis of the results by performing the data analysis using the most conservative approach of removing the data from individuals with missing outcome values from the analysis, or if it a missing value in a covariate, removing the covariate from the model. The results of the analysis with imputed data and complete data will be compared to assess whether they differ and both results will be reported. The analyses for aims related to longitudinal trajectory rely on statistical methods (mixed generalized linear models) that are robust to missing data at individual time points. In addition, all reasons for drop-out and missing data will be recorded and will be reported in all reports and publications (**MD-2, MD-3, MD-5**).

**Plan for analysis of COVID-19 Pandemic impact:** We propose to add the following steps to the data analysis in order to take the pandemic into account: 1) Analyze the patterns and

causes of refusal to participation in the study before and during the pandemic to determine if the populations in the two periods are coming from the same base population; 2) Analyze the patterns of missing data, comparing them between before and during the pandemic to determine whether we need to additionally add an indicator of the time of data collection (before or during pandemic) as another factor in the generation of the imputed outcome data; 3) analyze the primary and secondary outcomes in an intention-to-treat manner as proposed in the protocol. We will follow with another data analysis that will add in the model time of data collection (pre/post pandemic) and its interaction with intervention type as possible explanatory factors to determine the potential impact of change in timing of enrollment or unaccounted for changes in the intervention.

**Aim 1, Hypothesis 1:** Both the PART-O-17 and the QoLIBRI measures are numeric with a fairly large range that can be considered as continuous for data analysis. We will test the difference in means for PART-O-17 and QoLIBRI between the two groups at 6-month post-discharge using a two-sided t-test for independent samples. We will also test if the intervention has a long-term effect by comparing the two groups at 12-months post discharge using the same type of t-test.

**Aim 2, Hypothesis 2:** To compare the trajectory of improvement for 3-, 6-, 9- and 12-months post-discharge, we will plot individual trajectories over time and if it appears that the majority of people are leveling off over time we will consider a growth model. Otherwise, we will use a linear mixed model, with the outcome (PART-O-17 or QoLIBRI) as the response variable, and time and other factors (such as age, sex, race/ ethnicity, education, injury severity) as explanatory variables, and add intervention group and its interaction with time to test whether the interventions and time had an effect in the trajectory of the outcome.

**Aim 3, Hypothesis 3:** To compare the healthcare utilization in the first-year post discharge, the two groups will be compared on the distribution of categories of completed planned outpatients visits (less than 50%, between 50 and 75%, and more than 75%) by using a Chi-Square test. Both, the number of urgent care visits and the number of unplanned hospitalizations will be compared by means of a Poisson regression, which will include group and possibly adjusting for other factors (age, sex, race/ethnicity, education, injury severity). A statistically significant coefficient for intervention groups will show that the two groups differ in emergency and unplanned medical visits.

**Aim 4, Hypothesis 4a:** To compare caregiver burden, HRQOL, and satisfaction with roles and activities, we will apply t-tests for difference of means for independent samples for those measures that are found to have a normal distribution. We will also conduct heterogeneity of treatment effects analyses as we planned for other measures.

**Aim 4, Hypothesis 4b:** Using the Bakas Caregiving Outcomes Scale, Zarit Burden Interview, Sf-12, and the PROMIS Satisfaction with Social Roles and Activities for caregivers at 3-, 6-, 9- and 12-month follow-ups as response variables, we will fit a linear mixed model or growth model similar to the ones in hypothesis 2.

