***Outcomes Assessment:***

Early engagement with patients, family and other stakeholders revealed that survivors of TBI are primarily concerned about: (1) returning to pre-injury roles and activities and (2) regaining quality of life. We chose the Participation Assessment with Recombined Tools-Objective 17 (PART-O) and the Quality of Life after Brain Injury Scale (QoLIBRI) as primary outcomes because they capture content important to our stakeholders and are recommended by national TBI outcomes experts. Secondary outcomes will include assessment of healthcare utilization, caregiver burden, and process variables. Outcomes will be assessed at 3, 6, 9, and 12 months following discharge, with the primary outcome at 6 months. Analysis will be by intent to treat.

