### **Specific Aims and Hypotheses**

**Aim 1:** To compare the effectiveness of Standardized Discharge Care (SDC) as labeled in our original application and grant proposal, henceforth referred to as the “Rehabilitation Discharge Plan” (RDP), vs. SDC plus Optimized Transition Care (OTC) as labeled in our original application and grant proposal, henceforth referred to as “Rehabilitation Transition Plan” (RTP), RTP on improving patient-reported outcomes of (1) participation, as measured by the Participation Assessment with Recombined Tools-Objective 17 (PART-O-17) and (2) health-related quality of life, as measured by the Quality of Life after Brain Injury Scale (QoLIBRI), for individuals with moderate-to-severe TBI who are discharged from inpatient rehabilitation.

**Hypothesis 1:** Patients randomized to RTP will report better participation and health-related quality of life at the end of intervention (6-months post-discharge; **primary outcome**) and one year post-discharge compared to patients randomized to RDP.

**Aim 2:** To compare the trajectory of improvement across the first year post-discharge (with measurement at 3, 6, 9, and 12 months post-discharge) on patient-reported outcomes of (1) participation and (2) quality of life.

**Hypothesis 2:** Patients randomized to RTP will experience a steeper trajectory of improvement in participation and quality of life over 12 months compared to patients randomized to RDP.

**Aim 3:** To compare differences in healthcare utilization between RDP vs. RTP across the first year post-discharge.

**Hypothesis 3:** Patients randomized to RTP will complete a higher proportion of planned outpatient visits and have fewer urgent care visits or unplanned hospitalizations across the first year post-discharge, compared to patients randomized to RDP.

**Aim 4:** Caregiver outcomes: To compare the effectiveness of RDP vs. RTP on caregiver burden, health-related quality of life (HRQOL), satisfaction with roles and activities as measured by the Bakas Caregiving Outcomes Scale, the Zarit Burden Interview, SF-12, the PROMIS Satisfaction with Social Roles and Activities and assessment of Required Assistance and Time Spent Caregiving.

**Hypothesis 4a:** Caregivers of patients randomized to RTP will report lower caregiver burden at 6-months post-discharge, compared to caregivers of patients randomized to RDP.

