For the subgroup analysis, the models for the primary outcome variables (Part-O and QoLIBRI) will include the intervention group, all the covariates that define the subgroups, and interactions between each covariate and the intervention group. Test of interactions will reveal if there are subgroups based on a certain covariate (or factor) that respond differently to the RDP or RTP intervention. It is possible that for some covariates, we will not have enough individuals to give information on the outcomes variation in a certain subgroup and that we will not be able to assess the effect for that covariate, while for other covariates, the sample size in each subgroup will be enough to provide information for the data analysis. These numbers cannot be determined a priori. For example, facility discharges are expected to occur in approximately 198 participants (22%) of our sample which will allow adequate sample size for comparison, and males are expected to make up approximately 612 participants and can be compared to females. We may have difficulty comparing race/ethnicity on more specific subgroups such as Asians (expected to be approximately 2% of our participants) and Hawaiian/Pacific Islander (expected to be <1%), but will likely have an adequate sample size to compare Hispanic (11%) to non-Hispanic and Black (17%), White (73%), and other (10%). In this situation, we may have to collapse the categories into a smaller number, such as White, non-Hispanic Black, Hispanic, and Other. Given multiple insurance options across the population as well as across the sites we may not have adequate power to detect differences between every provider, but will explore the effect of relevant subgroups such as private insurance vs. Medicaid vs. Medicare, for example.

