We will explore the effects of the intervention on patient subgroups defined by factors known or hypothesized to have associations with poorer TBI outcome: facility vs. community discharge, race/ethnicity (White, non-Hispanic Black, Hispanic, Other), age (as continuous), male vs. female, lack of or lower degree of caregiver involvement (yes or no), severity of TBI (moderate vs. severe), presence of pre-injury psychosocial limitations (e.g., unemployment, substance abuse, categorized in yes or no) and medical or psychiatric comorbidity (yes or no), as well as study site, resource variability and insurance type (private insurance vs. Medicaid vs. Medicare). These factors will be entered in a single linear regression model in addition to the intervention group, using PART-O-17 as the response variable. Interactions between each factor and the intervention group will be entered in the model and test of interaction will be the test of heterogeneity. Before constructing the model, we will assess whether the explanatory variables (factors) are correlated to each other.

When two or more variables are deemed highly correlated, to avoid problems with collinearity, we will construct the model with the variable that provides the best model (from fit and diagnostic tests).

From previous research, we hypothesize that severity of TBI and presence of pre-injury psychosocial limitations will interact with the intervention group. With our expected sample size, we anticipate being able to address these questions. Some of the factors might not have a statistically significant effect, but have the effect in the expected direction. Effect sizes and confidence intervals will be calculated to express the potential effect of those factors. The results of these analyses will be valuable in designing future studies.

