#### *Primary Outcomes*

Aims 1 and 2 will address the primary outcomes of 1) Participation in Usual Roles and Activities: Participation Assessment with Recombined Tools-Objective 17 (PART-O) and 2) Health-related Quality of Life: Quality of Life after Brain Injury Scale (QoLIBRI)

Participation Assessment with Recombined Tools – Objective 17 (PART-O-17): Since the resumption of life roles and re-integration into the community drives patient and family decisions regarding rehabilitation care, community participation, as measured by the PART-O-17, was chosen as the primary outcome variable in the current study(**RQ-6, PC-1, PC-3**). The PART-O-17 is a patient-reported (or family member proxy-reported) measure of the International Classification of Functioning (World Health Organization) construct of “participation,” which is defined as involvement in life situations at the societal level as reflected in fulfillment of developmentally and culturally appropriate roles such as worker, student, spouse, parent, or citizen. All major conceptual models of disability (see, for example, Institute of Medicine’s Disablement Model) place considerable emphasis on fulfillment of social roles similar to the manner in which participation is defined in the International Classification of Functioning. The PART-O instrument is based on items derived or modified from three measures most commonly found in the TBI literature: Community Integration Questionnaire; Participation Objective, Participation Subjective; and the Craig Handicap and Assessment Reporting Technique.

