### **Planning the Study**

The present study design is informed by over 20 years of patient-centered research conducted by our team, extensive literature review, and input from focus groups and individual and group meetings with our Patient and Family Stakeholder members. Patient and Family Stakeholders provided critical input on how the interventions should be delivered. The investigators were enthusiastic about using the telephone, as well as computers and mobile devices to deliver the interventions. However, several patient partners pointed out that knowing who to contact in case of problems was a significant concern. This led to us ensuring all parties had access to the TCM via telephone during regular business hours, and making sure all key contacts will be included in the TBI Care Plan. Another patient partner emphasized the importance of helping them connect with and inform their primary care provider about their TBI. Consequently, we have included primary care in our Professional Stakeholder group and will ensure that the discharge plan is communicated to each patient's primary care provider.

The upshot of these conversations has been that transition care must be flexible and tailored to individual patient needs and preferences. As we meet in the future we are certain to discover other ways the protocol will need to be adapted to the needs of this patient population.

Meetings with Patient and Family Stakeholders also led to the decision to have two primary outcomes: participation in roles and activities and quality of life. Input from clinician stakeholders, which included primary care, confirmed the notion that existing systems of care are inconsistent and inadequate to meet the requirements of people with TBI and that efficient, well-defined case management models of care should be used to facilitate a comprehensive TBI care plan to help those in need. Our patient partners and stakeholders all agreed that the lack of consistent and evidence-based patient-centered guidelines required the inclusion of at least 2 comparators: one that used a brief in-hospital approach and one that used a remote, temporally extended case management approach.

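### PART-O-17 and QoLIBRI are both called primary and each is tested at 0.05, but the documents give no rule for success; two power statements also need a minor correction

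*Combined protocol and SAP*

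**What the plan says.** **Two primary outcomes.** The Abstract (Outcomes Assessment) selects PART-O-17 and QoLIBRI "as primary outcomes because they capture content important to our stakeholders". Planning the Study records "the decision to have two primary outcomes: participation in roles and activities and quality of life". The Primary Outcomes section begins "Aims 1 and 2 will address the primary outcomes of 1) Participation in Usual Roles and Activities" and lists QoLIBRI second. Heterogeneity of Treatment Effects says "the models for the primary outcome variables (Part-O and QoLIBRI) will include the intervention group".

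**Wording that points elsewhere.** The Primary Outcomes section also says that participation, measured by PART-O-17, "was chosen as the primary outcome variable in the current study". Hypothesis 1 joins the two outcomes: "Patients randomized to RTP will report better participation and health-related quality of life at the end of intervention".

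**Tests and levels.** Under Aim 1 of the Data Analysis Plan, each outcome has a two-sided independent-samples t-test at 6 months, repeated at 12 months. Aim 2 models the trajectory of both. The general approach paragraph states "We will use a significance level of 0.05 for all the analyses we will perform". It declines to adjust the other tests because power for the primary outcome is extremely high and small p-values are expected, and it promises caution with non-primary outcomes. Power for Secondary Outcomes, in both the original and the January 2019 form, powers three utilisation counts at 0.017, that is 0.05/3.

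**Power.** The 2019 update gives 0.80 power for a total of 300 at an effect size of 0.3. The general approach paragraph claims full power for PART-O-17 for any difference that exists.

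**The concern.** Suppose PART-O-17 is significant at 6 months and QoLIBRI is not, or the reverse. The documents do not say whether RTP has then succeeded, and the reading could be settled after the results are known. The error rate attached to a claim of success depends on which reading is used.

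The reason for not adjusting is also unsound. Power describes what happens when an effect exists; it puts no limit on false positives when there is none. Finally, the stated power figures make the primary comparison look safer at small samples and small effects than the plan's own inputs allow.

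**Working it through.** **1. What each reading implies for error.** Inputs: two tests, two-sided 0.05 each (general approach; Aim 1). The correlation between the test statistics is not given, so a range is assumed.

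- Either win counts, independent tests: 1 − 0.95² = 0.0975 two-sided. False wins favouring RTP only: 1 − 0.975² = 0.0494, against 0.025 for a single test.
- Either win counts, bivariate normal with limits ±1.96:

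| Assumed correlation | Two-sided | Favouring RTP |
|---|---|---|
| 0 | 0.0975 | 0.0494 |
| 0.5 | 0.0907 | 0.0454 |
| 0.7 | 0.0835 | 0.0417 |
| 0.9 | 0.0704 | 0.0352 |

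- Both required, fixed order, or PART-O-17 alone: at most 0.05 two-sided.

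**2. The utilisation counts.** 0.05/3 = 0.0167, the 0.017 of the power sections. The analysis section sets 0.05 for everything, so the level powered is not the level planned for testing.

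**3. Power for the primary comparison.** Formula (normal approximation, 1:1): power = Φ(d·√(N/4) − 1.96). Exact values use the noncentral t.

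- The original Power Analysis, N = 500, d = 0.5: Φ(5.590 − 1.960) = 0.9999. Its claim of practically full power reproduces under those conditions.
- The 2019 update, N = 300, d = 0.3: Φ(2.598 − 1.960) = Φ(0.638) = 0.738; noncentral t 0.736. The stated 0.80 does not reproduce. A one-sided test gives about 0.83, and 300 per arm gives 0.956, so neither explains it.
- N for 0.80 at d = 0.3: 4(1.960 + 0.842)²/0.3² = 349, or 350 in equal arms; 352 by the t distribution. The caregiver part of the same update gives 350 for this effect size and power.
- At the expected numbers, d = 0.3: 0.98 with 720 (80% of 900) and 0.99 with 900.

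**4. Effect detectable at 80% power with N = 720** (the plan's SD of 0.75; t-based):

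- alpha 0.05: 0.209 SD; 0.209 × 0.75 = 0.16 points.
- alpha 0.025 (Holm's worst case): 0.230 SD; 0.230 × 0.75 = 0.17 points. If both outcomes have the same effect, Holm needs only about 0.215–0.221 SD (assumed correlation 0 to 0.9).

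**The case against.** The best defence is that a rule is implied. Hypothesis 1 says 'and', which suggests that both are required; the singular in Primary Outcomes suggests PART-O-17 alone. Each removes the inflation. But they are different rules, neither is stated as a success criterion, and Planning the Study records a deliberate decision to have two primary outcomes.

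Several counterpoints stand:

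- Not every singular is evidence. In the Abstract and Hypothesis 1, 'primary outcome' marks the 6-month time point for both measures.
- The heterogeneity section names both outcomes as primary and then describes a model "using PART-O-17 as the response variable". That is a separate inconsistency and does not decide the success rule.
- The Manual of Procedures is to contain planned analysis procedures. It is not among these documents, so the finding is limited to what they state.
- The promise of caution covers non-primary outcomes. It does not help with two primary ones.

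A reader might infer that the trial runs a primary error rate near 10%. The documents do not support that: no passage says that either win suffices, and the figure counts false findings in both directions. A reader might also infer from the wrong 2019 figure that the trial is underpowered. It is not, at the plan's own effect sizes and expected numbers.

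**Conclusion.** The point holds as a missing decision rule that should be fixed. Any excess error is conditional on an either-wins reading: 7.0–9.75% two-sided, or 3.5–4.9% favouring RTP against 2.5% nominal, with the correlation assumed. Under the other readings there is none. The justification by high power is invalid on every reading, and the blanket 0.05 contradicts the 0.017 used for the utilisation counts.

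The power corrections are minor. The 0.80 should be 0.74, and the claim of full power omits the conditions under which it was derived (effect size of about 0.5 or more, at least 500 patients). The figures at 720 assume that all 720 have 6-month PART-O-17 data. That may be optimistic, because a questionnaire counts as followed once started, with no minimum of answered items.

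**What to change.** **Rule.** In the general approach paragraph, delete the reason based on high power and small expected p-values. There and under Aim 1, state one rule for the two 6-month tests. The choice belongs to the sponsor and stakeholders:

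- Holm: smaller p-value at 0.025, then the other at 0.05 only if the first is significant.
- Fixed sequence: PART-O-17 at 0.05, then QoLIBRI at 0.05 only if PART-O-17 is significant.
- Success only if both are significant at 0.05.

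State that the 12-month and trajectory tests of these outcomes are supportive and outside the rule. Give the three utilisation counts one level: either analyse at 0.017 or restate their power at 0.05. Call the remaining non-primary tests unadjusted and supportive.

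**Disclosure.** Date the rule. Say that it follows the scheduled end of follow-up (10/31/2022, Appendix 1), whether it precedes the analyses due 7/15/2023, and whether anyone choosing it had seen results by arm. The DSMB closed session allows the study statistician to run unblinded analyses, so this must be stated and not assumed.

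**Power text.** In the 2019 update write: *a total of 300 has 0.74 power for d = 0.3; about 352 are needed for 0.80.* Replace the claim of full power with: *If 720 patients have 6-month PART-O-17 data, power is 80% for about 0.21 SD (0.16 points at SD 0.75) at alpha 0.05; under Holm the worst case, with the first test at 0.025, is about 0.23 SD (0.17 points).*

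**Cost.** No new data or patients. At N = 720 there is essentially no power loss at the plan's d = 0.5. Holm's worst-case power falls from 0.98 to 0.96 at d = 0.3, and from 0.76 to 0.67 at d = 0.2, an assumed value that the plan does not use. Under a fixed sequence, QoLIBRI cannot be claimed alone. Requiring both gives joint power of 0.96–0.97 at d = 0.3 and 0.59–0.71 at d = 0.2 (equal effects, correlation 0 to 0.9). QoLIBRI will have fewer responses because proxies do not complete it, and the documents give no power calculation for it. A rule added this late is weaker than one fixed before data collection, hence the disclosure.
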